9.4.1. Primary Safety Analyses

9.4.1.1. Growth Velocity

Height assessments will be conducted at the following clinic visits: Visits 1, 3, and 5 during the 16-week baseline period; Visits 6-9, 12, 15 and 18 during the 52-week double-blind treatment period; and Visit 20 during the 8-week follow-up period. For each height assessment at a given clinic visit, triplicate stadiometry measurements will be collected for each subject. For the purposes of these analyses, each set of triplicate measurements will be averaged to derive one estimated height per subject per visit.

For each study period (baseline, double-blind treatment, and follow-up), growth velocity (cm/yr) will be calculated for each subject based on stadiometry data by fitting a regression line to all height measurements recorded for that subject during the period and determined by the slope of the fitted regression line. These will be calculated for the Growth population and for the ITT population and details of the calculations will be provided in the RAP. Baseline, double-blind treatment and follow-up growth velocities will be summarised by treatment while statistical analysis will only be performed for the double-blind treatment period.

The primary population for the primary growth analysis will be the Growth population (Section 9.3.1). The primary analysis will evaluate the primary de facto estimand: the mean difference in growth velocities between treatment groups over the double-blind treatment period, regardless of whether or not the subject remained on-treatment after their third post-randomization visit. For subjects in the Growth population who discontinue study treatment early after their third post-randomization clinic visit, all available on- and off- study treatment height assessments available during the treatment period will be included in the primary analysis. An ANCOVA model will be used to estimate the mean treatment difference in growth velocity over the double-blind treatment period, adjusting for baseline growth velocity, age at Visit 1, gender, and

country. A 95% confidence interval will also be provided for the mean treatment difference in growth velocity over the double-blind treatment period.

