Given subjects who discontinue study treatment may be administered other medications that may affect growth, a supportive analysis will be performed to evaluate the following de jure estimand: the mean difference in growth velocities between treatment groups over the double-blind treatment period, based on data measured while subjects are taking study treatment. This will be estimated using the Growth Population (Section 9.3.1) and using all on-treatment height measurements obtained up to the point of study treatment discontinuation.

Additional supportive analyses will be provided for the following subsets of the Growth Population:

1. Excluding subjects who exhibit greater than or equal to Tanner Stage 2 characteristics at any point during the treatment period or follow-up period
2. Excluding subjects who have questionable height measurements (definition of questionable measurements will be provided in the RAP)
3. Excluding subjects who have height measurements taken after receiving *rescue* systemic corticosteroids during the treatment period
4. Excluding subjects who have height measurements taken after receiving *rescue* inhaled and/or intranasal and/or systemic corticosteroids during the treatment period
5. Excluding subjects who have any of the above

A supportive completers' analysis of growth velocity over the 1-year double-blind treatment period, based on subjects in the Growth Population who completed the double-blind treatment period and remained on study treatment during that period, will also be performed.

Additional supportive analyses evaluating the primary de facto estimand, including all subjects (using the ITT Population, Section 9.3.1) will be performed. Further details will be provided in the RAP.

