4. ANALYSIS POPULATIONS

Population	Definition / Criteria	Analyses Evaluated
Total	
 Comprised of all participants screened and for whom a record exists on the study database. 	
 Study Population Safety
Intent-to-Treat (ITT)	
 Comprised of all randomised participants who receive at least one dose of study treatment. This population will be based on the treatment to which the participant was randomised. Any participant who receives a treatment randomisation number will be considered to have been randomised. 	
 Study Population Safety (including Growth Analyses) Efficacy
Growth	
 Comprised of all ITT participants who have stadiometric height assessments from at least three post-randomisation, on-treatment clinic visits (i.e., including all available height measurements after Visit 5 up to and including Visit 18, without exclusion) during the double-blind treatment period. Note: To be included in the Growth population, the 1st and 3rd height measurements need to be at least 7 weeks apart. 	
 Study Population Safety (i.e., Growth Analyses)

Refer to [Appendix 9](#): List of Data Displays which details the population used for each display.

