5.2. Baseline Definitions

In general, the baseline study period will be defined as an aggregate of measurements recorded during the period between screening and randomisation (Visits 1 – 5). Specific details follow below.

Baseline growth velocity

Each participant's baseline growth velocity (cm/yr) will be calculated based on the stadiometric height measurements recorded at Visits 1, 3, and 5. These data will be used to fit a simple linear regression line against time. The slope of the fitted regression line will be the participant's baseline growth velocity. Note that baseline growth velocity will be derived if there are baseline stadiometric height assessments from at least two clinic visits. Otherwise baseline will be missing.

Baseline height standard deviation score (SDS)

Each participant's Visit 5 height standard deviation score will serve as the baseline height SDS. Height standard deviation scores will be calculated as described in Section 11.6.3.

Baseline eDiary measures

Baseline PEF will be defined as the average of the measurements recorded on the morning of randomisation (Visit 5) and on the previous 6 days.

The average daily rescue medication used over the last 7 days prior to randomisation, including the rescue medication use recorded on the morning of randomisation, will be used as the baseline value.

The baseline percentage of rescue-free 24-hour periods will be defined as the percentage of 24-hour periods in the 6 days prior to randomisation and on the day of randomisation in which a participant used no rescue medication. Percentage rescue-free 24-hour periods will be calculated as described in Section 11.6.5.

The baseline percentage of symptom-free 24-hour periods will be defined as the percentage of 24-hour periods in the 6 days prior to randomisation and on the day of randomisation for which a participant's daytime asthma symptom score and night-time symptom score is 0. Percentage symptom-free 24-hour periods will be calculated as described in Section 11.6.5.

Baseline C-ACT score

Each participant's Visit 5 C-ACT score will serve as the baseline score.

Derivations and handling of missing baseline data

If the baseline for an endpoint is missing it will not be imputed using a different time point or derivation but will remain missing. For example, if there is no C-ACT value available at Visit 5, then baseline C-ACT will be missing.

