7.1.5.1. Statistical Methodology Specification

Endpoint / Variables

 Growth velocity (cm/yr) over the double-blind treatment period as determined by stadiometry. For details of growth velocity calculation see Section 11.6.3.
Model Specification

 The primary endpoint will be analysed using an analysis of covariance (ANCOVA) model adjusting for baseline growth velocity (continuous, see Section 5.2: Baseline Definitions), age at Visit 1 (continuous), gender (categorical), and country (categorical).

 • The primary analysis will include all available height data, regardless of any intercurrent events (defined in Section 7.1.4) that occur during the study. • Missing data will be assumed to be missing at random (MAR) and will not be imputed. The mean difference in growth velocity over the treatment period between treatments and a 95% confidence interval will also be provided.

Model Checking & Diagnostics

 • The Kenward and Roger method [Kenward, 1997] of approximating the denominator degrees of freedom and correcting for bias in the estimated variance-covariance matrix of the fixed effects will be used in the diagnostic analyses of ANCOVA models. The Kenward-Roger method will be invoked by specifying the DDFM=KR option in the PROC MIXED model statement. • Appropriate graphs will be reviewed as part of the model-checking process in order to ensure that distributional assumptions hold. Additional analyses may be considered if these assumptions are not met. These graphs will include a normal probability plot of the residuals and a plot of the residuals versus the fitted values. If there are any departures from the distributional assumptions, alternative models will be explored using appropriate transformed data.

Model Results Presentation

 • The point estimate of the mean treatment difference in growth velocity and corresponding 95% confidence interval will be presented for the comparison between treatment arms.

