Discontinuation of Randomised Treatment	Only available height data while the participant is on randomised double-blind treatment will be used in the analysis.								
Event	Handling Strategy								
Discontinuation of Randomised Treatment	Only available height data while the participant is on randomised double-blind treatment will be used in the analysis.								

Supportive Estimand VIII for Primary Endpoint
									

 • Another supportive estimand defined for the primary endpoint (as defined in Section 7.1.1) will be Supportive Estimand VIII. • This estimand will be based on the ITT Population (as defined in Section 4: Analysis Populations). • The summary measure will be as described in Section 7.1.2 for the primary analysis, and the statistical analyses/methods (i.e., model specification, model checking and diagnostics, and model results presentation) will be as described in Section 7.1.5 for the primary analysis. • The strategies for handling the intercurrent events/events leading to missing data for this estimand will be as described in Section 7.1.4 for the primary analysis. 									

Supportive Analyses - Assessing Missing Data
									

 • Two approaches have been defined to assess the effects of missing data. For these analyses the population of interest will be the Intent-to-Treat (ITT) population, as defined in Section 4: Analysis Populations. • In cases where the final height measurement at week 52 is missing, these missing height data will be imputed using Multiple Imputation (described at length in Section 11.7.2) by applying to the last available height measurement the following sets of rules: 
 1. Use the ‘worst growth rate’ (i.e., smallest growth velocity) from participants from the FF 50 treatment group who complete the double-blind treatment period as the central value for imputations of missing data in the FF treatment group, and the ‘worst growth rate’ from participants from the placebo group who complete the double-blind treatment period as the central value for imputations of missing data in the placebo treatment group. 2. Use the ‘worst growth rate’ (i.e. smallest treatment velocity) from participants from the FF 50 treatment group who complete the double-blind treatment period as the central 									

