7.2.2. Change from Baseline in Growth Velocity Quartiles

Shifts from baseline to endpoint in growth velocity percentile based on quartiles will be summarized by treatment group. Baseline is defined as the baseline study period (see Section 5.2: Baseline Definitions); endpoint is defined as the last 12 weeks of the double-blind treatment period. Participants with a decrease in growth velocity quartile from baseline to endpoint will be listed. Details of the calculation of these quartiles can be found in Section 11.6.3. This characterization of growth velocity will be based on all available on- and off-treatment height data.

No formal statistical analysis is planned.

7.2.3. Analysis of Growth Velocity Over the First 12 Weeks of the Double-Blind Treatment Period

Growth velocity during the first 12 weeks (~10 to 13 weeks given visit windows, [Appendix 2: Schedule of Activities](#)) of the double-blind treatment period will be analysed (Supportive Estimand XI). Regarding the intercurrent event of “*Discontinuation of Randomised Treatment*”, all available height data collected during the double-blind treatment period up to Visit 8 while the participant is on randomised double-blind

treatment will be considered. In order to be included in this analysis, a participant must have data from a Visit 8 (Week 12) stadiometric height assessment.

An analysis of covariance (ANCOVA) model, similar to the one defined for the primary analysis, will be used to estimate the mean treatment difference in growth velocities over the first 12 weeks of the double-blind treatment period. The summary measure, statistical analyses/methods (i.e., model specification, model checking and diagnostics, and model results presentation), and strategies for handling all other intercurrent events/events leading to missing data will be as described in Section 7.1: Primary Growth Analyses. By-treatment summaries of growth velocity during the baseline period and the first 12 weeks of the double-blind treatment period will also be provided. The change from baseline in growth velocity will also be summarised.

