11.6.3. Growth Data

Triplicate stadiometric height measurements, as well as the average of each set of triplicate measurements, will be collected at each planned visit according to the Protocol Defined Schedule of Events (see Section 11.2.1). The average will serve as the participant’s height at that clinic visit.

Growth Data
Growth Velocity Calculation

 • Growth velocity will be calculated for each participant over each study period (i.e., baseline, double-blind treatment, and follow-up) by fitting a regression line to the height measurements recorded for that participant during the period. The slope of this regression line will be the participant’s growth velocity for that study period. • Stadiometric height measurements obtained at Visits 1, 3, and 5 will be used to determine the baseline period growth velocity, which will be calculated based on data from at least two of these visits. • Stadiometric height measurements obtained at Baseline (Visit 5) and during the double-blind treatment period (Visit 6 up to and including Visit 18) will be used to determine the double-blind treatment period growth velocity. Separate estimands for growth velocity during the double-blind treatment period will be considered in the Growth and ITT populations (as defined in Section 7.1: Primary Growth Analyses). • Stadiometric height measurements obtained at Visits 18 and during the follow-up period will be used to determine the follow-up period growth velocity. • Stadiometry measurements obtained during the Early Withdrawal/Early Treatment Discontinuation Visit will be included in the calculation of the growth velocity over the double-blind treatment period.
Growth Velocity Below the 3rd Percentile

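### The non-US growth ANCOVA drops country, the randomisation stratum, and Supportive Estimand VIII gives very short ITT slopes full weight with no information-weighted ITT check; both effects look small.

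*SAP*

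**What the plan says.** **Regional model.** SAP 7.2.5 fits separate ANCOVAs for US and non-US sites, like the primary model but with country removed from the covariates. SAP 2.3 stratifies randomisation by country and names six countries at start-up: the United States, Argentina, Poland, Romania, Russia and South Africa. Protocol 4.4 gives possible differences in growth velocity between countries as one reason for stratifying. SAP 5.3 pools any country with fewer than 12 ITT participants.

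**Estimand VIII.** SAP 7.1.6 states: "This estimand will be based on the ITT Population (as defined in Section 4: Analysis Populations". The model comes from SAP 7.1.5 and the missing-data handling from 7.1.4: one least-squares slope per child, ANCOVA with no weights stated, no imputation. ITT requires only randomisation and one dose. The slope includes Visit 5, and under SAP 11.6.3 "Stadiometry measurements obtained during the Early Withdrawal/Early Treatment Discontinuation Visit will be included in the calculation of the growth velocity" over the treatment period.

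The SAP sets minimum data elsewhere:
- Growth Population (SAP 4): at least three post-randomisation on-treatment visits, and "the 1st and 3rd height measurements need to be at least 7 weeks apart".
- Baseline (SAP 5.2): "baseline growth velocity will be derived if there are baseline stadiometric height assessments from at least two clinic visits".
- 12-week analysis (SAP 7.2.3): "a participant must have data from a Visit 8 (Week 12) stadiometric height assessment".

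No such rule applies to the ITT treatment-period slope. Protocol 9.4.1.1 says of the velocities: "These will be calculated for the Growth population and for the ITT population and details of the calculations will be provided in the RAP". The model that weights children by information, the random-coefficient model of SAP 7.2.7 (Table 2.36), is run on the Growth Population only.

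**The concern.** A slope over a few weeks, expressed per year, magnifies height error greatly, yet counts in Estimand VIII as much as a slope from eight visits over a year. VIII is the all-subjects counterpart of the primary analysis. If the two differ, the reader wants to know whether a handful of noisy slopes or the Growth Population exclusions caused it. No pre-specified ITT analysis separates noise under the same missing-at-random assumption. Estimand IX extends records without a Week 52 height to day 365, but by worst-growth imputation. Estimand X leaves placebo slopes as observed.

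The diagnostics section does not close the gap. It says "If there are any departures from the distributional assumptions, alternative models will be explored using appropriate transformed data", and a transformation keeps the equal weights.

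The regional point is separate. Dropping country is harmless in the US model, where it is constant. In the non-US model it puts between-country variation into the residual and ignores the factor by which the children were randomised.

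**Working it through.** **Inputs from the documents.** SD of growth velocity 1.2 cm/yr; 203 evaluable and about 225 randomised per arm; target CI width at most 0.5 cm/yr (Protocol 9.2.1). Stadiometry during treatment on days 1, 29, 57, 85, 113, 197, 281 and 365 (Protocol 7.1).

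**Assumptions, not in the documents.** Error SD of a visit-mean height 0.2 cm (range 0.1-0.3). Short records end evenly over days 15-57, with the day-29 height included when earlier. Share of short records p, with 1-2% as the main range. Between-country SD s of 0.2-0.4 cm/yr.

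**Plan's own figure.** Width = 2 × 1.96 × 1.2 × sqrt(2/203) = 0.467, within the 0.5 target. With 225 per arm it is 0.443.

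**Slope error.** SE = error / sqrt(Σ(t − t̄)²), t in years.
- Full schedule: Σ = 0.8698, so SE = 0.2/sqrt(0.8698) = 0.21 cm/yr (0.11-0.32).
- Visits 5 and 6 only (28 days): Σ = 0.002938, so SE = 3.7 cm/yr (1.8-5.5).
- Error-variance ratio: 0.8698/0.002938 = 296, whatever the error size.

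**CI width for Estimand VIII.** Between-child variance B = 1.44 − SE_full². Width = 2 × 1.96 × sqrt(2 × [(1−p) × 1.44 + p × (B + mean SE_short²)]/225).

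Example at 0.2 cm and p = 2%: B = 1.394 and mean SE_short² = 13.61, so the bracket is 0.98 × 1.44 + 0.02 × 15.00 = 1.711 and the width is 0.48.

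| Short share p | Children per arm | 0.1 cm | 0.2 cm | 0.3 cm |
|---|---|---|---|---|
| 0 | 0 | 0.44 | 0.44 | 0.44 |
| 1% | about 2 | 0.45 | 0.46 | 0.49 |
| 2% | about 4-5 | 0.45 | 0.48 | 0.53 |
| 5% | about 11 | 0.47 | 0.54 | 0.64 |
| 10% | about 22 | 0.49 | 0.62 | 0.78 |

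**Timing matters.** If short records end only at scheduled visits, half on day 29 and half on day 57, mean SE_short² at 0.2 cm falls to 8.51. The widths at 2, 5 and 10% become 0.47, 0.50 and 0.56.

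**Weighted comparison.** With information 225 × [(1−p)/1.44 + p × mean(1/(B + SE_short²))] per arm, the width stays near 0.45 at 1-2%. A 28-day child then gets 1.44/(B + SE²) = 10% (4.5-30%) of a full-schedule child's weight. The chance gap between VIII and the weighted estimate, sqrt(unweighted variance − weighted variance), has SD 0.05 (0.02-0.07) cm/yr at 2%.

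**Early-effect illustration.** Suppose a 0.48 cm deficit built up evenly over 12 weeks and then stopped. The slope difference would be −0.37 on the full schedule and −2.09 on short records. At 2%, VIII would shift by 0.02 × (−2.09 + 0.37) = −0.03 cm/yr, about the size of the chance gap.

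**Country.** If the 1.2 SD includes between-country variation, the widening from omitting country is sqrt(1.44/(1.44 − s²)): 1.014 at s = 0.2 and 1.061 at s = 0.4.

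**The case against.** **Existing displays.** Several ITT outputs already bear on short slopes: attendance by visit (Table 1.13), velocity summaries (Table 2.18, to set beside Table 2.2), missing heights by visit and arm (Table 2.24), Figure 2.4, Listing 24 and the residual plots. This stands in large part. Extreme slopes would probably be noticed. None of the titles or notes in SAP Appendix 9 describes a count of heights or span behind each slope. The mock shells of SAP Appendix 10 were not available, so a count inside a shell cannot be ruled out.

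**Rarity.** A reader might infer a 5-10% share of short records from the protocol's allowance of up to 10% withdrawal by week 12. The documents do not support that. The allowance concerns study medication, and Protocol 5.5.1 keeps such children for height measurement. Study withdrawal is limited to withdrawn consent or loss to follow-up, and a child lost before Visit 6 would often have no later height, hence no slope. The 5% and 10% rows are therefore sensitivity figures only.

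**The check does not discriminate by itself.** This stands. The weighted model largely discounts the children in question, and a gap may be real. Protocol 4.4 expects the greatest effect in the first few months, although the review cited in Protocol 4.6.1 found no overall effect in the first three. The 7.2.7 model also omits country and baseline growth velocity, so covariates may contribute to a gap.

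**Country.** It concerns another analysis and the gain is small. Both are true, but it changes a stated rule at almost no cost.

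**Conclusion.** Both points hold as modest improvements to supportive analyses.

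Omitting country from the non-US ANCOVA costs about 1-6% of CI width, if the assumed between-country SD of 0.2-0.4 cm/yr is right. A reader might infer bias. Stratified randomisation gives no reason to expect it, so the loss is one of precision.

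For Estimand VIII, 1-2% short records would take the CI width from 0.44 to about 0.45-0.53 cm/yr, under the assumed error and timing. At 0.1 cm error the change is negligible.

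Two stronger readings are not supported. The primary result is not put in doubt, because the three-visit and 7-week rules keep such slopes out of it. Nor does VIII need a minimum span, since the protocol says "Additional supportive analyses evaluating the primary de facto estimand, including all subjects (using the ITT Population, Section 9.3.1) will be performed"; a minimum would work against including everyone. Children who stop treatment but keep attending have full-length slopes and are not at issue.

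**What to change.** - **SAP 7.2.5:** keep country, pooled as in SAP 5.3, as a covariate in the non-US ANCOVA.
- **SAP 7.1.6:** leave Estimand VIII as specified. Also run the SAP 7.2.7 random-coefficient model on the ITT Population. Describe it as a check on noise from short slopes that gives those children little weight and assumes linear growth and data missing at random. It is not a test of the Growth Population exclusions.
- **Display:** report per arm the number of ITT children whose treatment-period slope uses fewer than three heights (counting Visit 5) or spans under 7 weeks, and read any gap beside it. This is slightly narrower than the range modelled above: records ending on days 50-57 would not be counted, but they are the most precise of that set.

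**Cost:** SAP wording, one covariate kept, one extra model run and one count per arm. The downside is a second ITT estimate that may differ from VIII for a real reason if the effect is concentrated early, so a gap must not be taken as proof of noise.
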